6.6. Subsequent Anti-Cancer Therapies

The number and percentage of subjects that received chemotherapy, immunotherapy, hormonal therapy, biologic therapy, radioactive therapy, small molecule targeted therapy, as post study treatment anti-cancer therapy will be summarized. Time from study treatment discontinuation to the first post study treatment anti-cancer therapy will also be included in this summary Table, if available.

Follow-up anti-cancer therapy will be coded using GSK Drug coding dictionary, then summarized by ingredient. A listing of the type of follow-up anti-cancer therapy received (chemotherapy, immunotherapy, hormonal therapy, biologic therapy, radioactive therapy, and small molecule targeted therapy for each subject will be provided).

7. EFFICACY ANALYSES

7.1. Part 1: Dose Escalation

7.1.1. Secondary Efficacy Analyses

7.1.1.1. Endpoint / Variables

BOR

Best Overall Response (BOR) is defined as the best confirmed response (stringent Complete Response [sCR] > Complete Response [CR] > Very Good Partial Response [VGPR] > Partial Response [PR] > Minimal Response [MR] > Stable Disease [SD] > Progressive Disease [PD] > Not Evaluable [NE]) from treatment start date until disease progression or initiation of new anti-cancer therapy, whichever is earlier, as assessed by the investigator per IMWG (2016). Details on derivation of confirmed response are provided in [Table 4](#).

ORR

Overall Response Rate (ORR), defined as the percentage of participants with a confirmed PR or better as the BOR (i.e., Partial Response [PR], Very Good Partial Response [VGPR], Complete Response [CR], and stringent Complete Response [sCR]), as assessed by the investigator per IMWG (2016).

ORR at interim analysis will be analysed based on confirmed responses, if available. However, in case a participant has achieved a response of PR or better at data cut, which was not confirmed due to the time constraints (too short timeframe for the next assessment), but with a potential to be confirmed through subsequent assessments after interim, the participant will also be considered as a responder; if the participant dies or discontinues study or starts other anti-cancer therapy prior to confirming the response, the participant will not be considered as a responder at IA.

Only the assessments from the start of treatment up to the earlier of confirmed disease progression or the start of new anti-cancer therapy will be considered. Only new systemic anti-cancer drugs taken are considered as anti-cancer therapy (radiotherapy and surgeries are not considered as systemic anti-cancer therapy for the purpose of this analysis).

Subjects with only assessments of Not Evaluable or missing response will be treated as non-responders; i.e. they will be included in the denominator when calculating the percentage.

Details on derivation of confirmed response are provided in [Table 4](#).

Table 4 Derivation of Confirmed Response

	Response at the First Time Point	Response at Subsequent Time Point¹	Confirmed Response at the First Time Point
1	sCR	sCR	sCR
2	sCR	CR	CR
3	CR	sCR/CR	
4	sCR/CR	VGPR	VGPR
5	VGPR	sCR/CR/VGPR	
6	sCR/CR/VGPR	PR	PR
7	PR	sCR/CR/VGPR/PR	
8	sCR/CR/VGPR/PR	MR	MR
9	MR	sCR/CR/VGPR/PR/MR	
10	sCR/CR/VGPR/PR/MR	SD	SD
11	sCR/CR/VGPR/PR/MR	PD (any reason) OR No subsequent disease assessment: subject died or discontinued study or started new anti-cancer therapy before further adequate disease assessment	SD
12	sCR/CR/VGPR/PR/MR/PD (due to reasons other than imaging, i.e., plasmacytoma or bone lesion)	No subsequent disease assessment: subject has not died, discontinued from study or (except for PD) started new anti-cancer therapy; but as yet has no further adequate disease assessments	Unconfirmed sCR/CR/VGPR/PR/MR/PD Will be categorized as NE for ORR analysis. For ORR analysis in IA, the UC response (PR or better) will be counted as responder.
13	PD (due to reasons other than imaging, i.e., plasmacytoma or bone lesion)	PD (any reason) including PD after initiation of new anti-cancer therapy OR	PD

	Response at the First Time Point	Response at Subsequent Time Point¹	Confirmed Response at the First Time Point
		No subsequent disease assessment: subject died due to PD before further adequate disease assessment (including death due to PD after initiation of new anti-cancer therapy)	
14	PD (due to reasons other than imaging, i.e., plasmacytoma or bone lesion)	sCR/CR/VGPR/PR/MR/SD OR No subsequent disease assessment: subject died due to reasons other than PD before further adequate disease assessment OR No subsequent disease assessment: subject discontinued study before further adequate disease assessment	NE
15	SD	Any OR No subsequent disease assessment	SD
16	PD due to imaging (plasmacytoma or bone lesion)	Any OR No subsequent disease assessment	PD
17	NE or missing	Any OR No subsequent disease assessment	NE

1 Subsequent disease assessment is defined as the next adequate (not missing or NE) disease assessment following the first timepoint before (or on the same date of) start of new anti-cancer therapy except for confirmation of PD, for which PD or death due to PD after new anti-cancer therapy are considered for confirmation of PD. No minimal time interval is required for the subsequent disease assessment but a different sample is required for confirmation.

2 SD does not need to be confirmed.

3 PD due to imaging (i.e., plasmacytoma or bone lesion) does not need to be confirmed.

Where criteria are not mutually exclusive, take the first that applies.

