Situation	Date of Event (Progression/Death) or Censored ¹	Event (Progression/Death) Or Censored
No adequate baseline assessments ⁴ and the subject has not died (if the subject has died follow the rules for death indicated at the bottom of the Table)	First dose	Censored
No post-baseline assessments and the subject has not died (if the subject has died follow the rules for death indicated at the bottom of the Table)	First dose	Censored
Progression documented between scheduled visits	Date of assessment of progression	Event
With post-baseline assessment but no progression (or death)	Date of last 'adequate' assessment of response ²	Censored
No adequate post-baseline assessment before start of new anticancer therapy	First dose	Censored
With adequate post-baseline assessment and new anticancer treatment started (prior to documented disease progression). ³	Date of last 'adequate' assessment of response ² (on or prior to starting anti-cancer therapy)	Censored
Death before first scheduled assessment (or Death at baseline or without any adequate assessments)	Date of death	Event
Death between adequate assessment visits	Date of death	Event
Death or progression after more than three missed scheduled assessment	Date of last 'adequate' assessment of response ² (prior to missed assessments): If the disease assessment is every 3 weeks, a window of 66 days (9 weeks + 3 day window) will be used to determine whether there is extended time without adequate assessment. If the time difference between PD/death and last adequate disease assessment is more than 66 days, PFS will be censored at the last adequate disease assessment prior to PD/death.	Censored

¹ Event or censored are based on confirmed responses.

² An adequate assessment is defined as an unconfirmed assessment where the investigator assessed response is sCR, CR, PR, VGPR, MR, or SD.

³ If PD and New anti-cancer therapy occur on the same day assume the progression was documented first e.g., outcome is progression and the date is the date of the assessment of progression).

⁴ Adequate baseline assessment is defined as at baseline, a patient has at least one of the following measurements: a. Serum M-protein ≥ 0.5 g/dL (≥ 5 g/L) or b. Urine M-protein ≥ 200 mg/24h or c. Serum FLC assay: Involved FLC level ≥ 10 mg/dL (≥ 100 mg/L) and an abnormal serum free light chain ratio (< 0.26 or > 1.65).

Table 6 Assignments for Progression and Censoring Dates for TTP Analysis

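### In PFS, TTP and DoR, a laboratory PD not confirmed before new therapy or study exit is an event only if PD or PD death is recorded later; otherwise the subject is censored before the progression

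*SAP*

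**What the plan says.** Table 4 (SAP 7.1.1.1) separates imaging PD from all other PD. "PD due to imaging (i.e., plasmacytoma or bone lesion) does not need to be confirmed", whereas any other PD (called laboratory PD here) does.

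- **Row 13** makes it a confirmed PD if the next finding is "PD (any reason) including PD after initiation of new anti-cancer therapy", or if the subject dies of PD with no further assessment.
- **Footnote 1** restricts the confirming assessment to one made up to and including the day new therapy starts, apart from later findings "for which PD or death due to PD after new anti-cancer therapy are considered for confirmation of PD". On timing it says: "No minimal time interval is required for the subsequent disease assessment but a different sample is required for confirmation".
- **Row 12** leaves the PD unconfirmed when the "subject has not died, discontinued from study or (except for PD) started new anti-cancer therapy; but as yet has no further adequate disease assessments".
- **Row 14** gives NE in several cases, among them "No subsequent disease assessment: subject discontinued study before further adequate disease assessment".

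SAP 7.2.2.1 builds the time-to-event endpoints on this. Footnote 1 of Tables 5 and 6 reads "Event or censored are based on confirmed responses". Footnote 2 of Table 5 reads "An adequate assessment is defined as an unconfirmed assessment where the investigator assessed response is sCR, CR, PR, VGPR, MR, or SD", and footnote 2 of Table 6 lists the same categories; PD is not among them. The DoR definition censors responders without confirmed PD at the Table 6 date.

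**The concern.** Whether a progression seen on study treatment counts as an event should not depend on what happens under a different treatment. Here it can. For a laboratory PD with no second sample before the switch, a poor outcome on the next therapy makes the PD an event, while a good outcome or no further assessment leaves it unconfirmed. The subject is then censored at a visit before the PD. Because the PD itself sets off this chain, the censoring is informative, and it removes observed progressions from the Kaplan-Meier estimates.

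At stake are the medians and quartiles of PFS, TTP and DoR and the PFS rates at 6 to 18 months (SAP 7.2.2.2). PFS and DoR are also headline displays (Tables 2.007 and 2.004 in SAP 16.11.5). The trial is single-arm, so no comparator carries the same bias. The SAP plans no sensitivity analysis that would show it.

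**Working it through.** **1. The rules applied to three constructed records.** Each subject has a last non-PD assessment on day 63, a laboratory PD on day 84, and no second sample before the next step.

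| Subject | After day 84 | Table 4 | PFS/TTP status |
|---|---|---|---|
| A | New therapy day 95, PD on it day 130 | Row 13: PD | Event, day 84 |
| B | New therapy day 95, responds or has no further assessment | Row 12: unconfirmed PD | Censored, day 63 |
| C | Leaves the study | Row 14: NE | Censored, day 63 |

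For a responder on the next therapy, rows 12 and 14 could both seem to fit. Table 4 says to take the first that applies, and neither row yields PD. The censoring date is day 63 rather than day 84 because PD is not an adequate assessment.

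A fourth record marks the boundary. If a second sample on or before day 95 again shows PD, row 13 applies and the event is on day 84 whatever follows.

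**2. Size.** The SAP states no PFS, TTP or DoR figure, so there is nothing to reproduce. The following inputs are assumptions:

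- 28 subjects (the planned Part 2 size);
- exponential PFS, true median 6 months;
- assessments every 21 days, the 3-week interval used in Table 5;
- 85% of events are PD;
- cut-off at 15 months;
- a share q of PDs left unconfirmed for good, each replaced by a censoring one visit (21 days) earlier.

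Typical results over 2,000 simulated trials per scenario:

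| q | Kaplan-Meier median (months) | 12-month rate |
|---|---|---|
| All PDs counted | 6.2 | 0.26 |
| 10% | 6.9 | 0.29 |
| 20% | 7.6 | 0.32 |
| 40% | 9.0 to 9.5 | 0.40 |

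Relative shifts of the median: 6.9/6.2 = 1.11, 7.6/6.2 = 1.23, and 9.0/6.2 = 1.45 to 9.5/6.2 = 1.53. With 3-weekly visits the median moves in steps of about 21/30.44 = 0.69 months.

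**3. Direction.** A second simulation took every event as PD, with follow-up of 15 to 24 months and 4,000 trials of 28 subjects at each share. The 12-month rate rose in 89% of trials at a 10% share and in more than 99.9% at 30%. Neither the rate nor the median fell in any trial. With 40,000 subjects and a 5% share, the 12-month rate rose by about 1 to 2 points.

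**4. Plausible range of q.** Take q as the product of three assumed shares: PDs that are laboratory (0.7 to 0.9), those with no second sample before the switch or exit (0.1 to 0.5), and those never confirmed later (0.3 to 1.0).

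- Low: 0.7 × 0.1 × 0.3 = 0.02
- High: 0.9 × 0.5 × 1.0 = 0.45

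**The case against.** The strongest reply is that the rule is narrower than it looks. A reader might infer that every laboratory PD followed by new therapy counts only if the next therapy fails. Table 4 does not say that: a second sample before or on the day of the switch settles the matter, with no minimum interval, and imaging PD needs no confirmation. Nor is failure of the next therapy strictly required, since any later PD finding, even an early one, or death due to PD is enough. Some subjects like B will therefore return to events with longer follow-up. This limits how many subjects are affected, not the mechanism.

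Other points on that side:

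- **Frequency.** A reader might suppose that moving to new therapy after one laboratory PD is common in this population. The SAP gives no figure, so q remains an assumption.
- **Discontinuation.** Row 14 concerns leaving the study. A subject who only stops treatment and stays in follow-up can still be confirmed.
- **Wording of Table 5.** Its new-therapy row speaks of therapy started before documented progression, and in B the PD was documented before the switch. Footnote 1 of Table 5 and the DoR text nevertheless point to confirmed PD. Footnote 3, which lets PD prevail when both fall on the same day, sits awkwardly with that. The ambiguity is itself worth removing.
- **Deaths.** For PFS, a later death from any cause may still be an event. Table 5 does not say whether the death row or the new-therapy row prevails.
- **Consequence.** These endpoints are secondary and descriptive, no decision rule rests on them, and listings would let a reader find the affected subjects.
- **Remedy.** Counting single-sample PDs outright as events brings in some that a second sample would not have confirmed. This stands, and it is why a sensitivity analysis is preferable to replacing the definition.

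**Conclusion.** The point holds for laboratory PDs not confirmed by the day new therapy starts or before study exit. For these, event status in PFS, TTP and DoR depends on later outcomes. Without later PD or PD death, the subject is censored before the observed progression, subject to the open question of later deaths in PFS. The resulting bias is upward.

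The size cannot be fixed from the SAP. Under the stated assumptions, one PD in ten affected adds about 0.7 months to a 6.2-month median and 3 points to the 12-month rate; four in ten add about 3 months and 14 points. At 5% or below the effect is small. The documents do not support extending the point to all laboratory PDs followed by new therapy, to imaging PDs, or to ORR.

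**What to change.** Keep Table 4 for BOR and ORR, and keep the confirmed-PD analysis of PFS, TTP and DoR. Then make two changes:

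1. **Sensitivity analysis.** Pre-specify one for PFS, TTP and DoR in which an investigator-assessed laboratory PD, followed by new anti-cancer therapy or study discontinuation with no adequate assessment in between, is an event at the first PD date whatever happens afterwards. Report it beside the main analysis with the number of subjects whose status changes.
2. **Table 5 wording.** State that documented progression there means confirmed PD, and say which row prevails when death follows new therapy.

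The cost is a few lines of SAP text and one further run of three existing displays, with no new data. The drawback is that some single-sample PDs that would not have been confirmed count as events in the sensitivity analysis, so its estimates may err slightly low.

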7.1.1.2. Summary Measure

ORR

The number and percentage of participants with the BOR in the following response categories at timepoint will be summarized: sCR, CR, VGPR, PR, overall response (sCR+CR+VGPR+PR), minimal response (MR), stable disease (SD), progressive disease (PD), and not evaluable (NE). The corresponding exact 95% CI for ORR will also be provided. Participants with unknown or missing responses will be treated as non-responders, i.e., these participants will be included in the denominator when calculating percentages of response. A list of investigator-assessed response at each visit will be listed.

A waterfall plot showing the maximum percent reduction from baseline in Serum M protein, or Urine M-protein, or difference between two types Serum FLC [Kappa light chain (Kappa LC) and Lambda light chain (Lambda LC)] for each subject will be produced using by dose level. The plot will be color-coded for M-protein types and Serum FLC, etc. Indication of the best overall response will be provided below the plot. Only the assessments from the start of treatment up to the start of new anti-cancer therapy will be considered. Only new systemic anti-cancer drugs taken are considered as anti-cancer cancer therapy (radiotherapy and surgeries are not considered as systemic anti-cancer therapy for the purpose of this analysis).

The maximum percent reduction will be plotted in the following hierarchical order:

- [1] Plot Serum M-protein maximum percent reduction from baseline if data is available;
- [2] If [1] is not feasible, plot Urine M-protein maximum percent reduction from baseline if data is available;
- [3] If both [1] and [2] are not feasible, plot maximum percent reduction from baseline for difference between two types of Serum FLC if data is available;

Difference between two types of Serum FLC

The percent change from baseline for difference between two types of Serum FLC is defined as:

$$(\text{post-baseline difference} - \text{baseline difference}) / \text{baseline difference} * 100\%$$

To calculate the difference, the “involved” and “non-involved” light chains must be determined at first based on the ratio of non-missing values for Serum Kappa LC protein and Serum Lambda LC protein at baseline.

The detailed algorithm is provided as below:

- If the baseline ratio of (Kappa LC/Lambda LC)>1.65, then Kappa LC is defined as involved FLC, and Lambda LC is defined as non-involved FLC. Then
 - Difference between involved and unininvolved = Kappa LC-Lambda LC
- If the baseline ratio of (kappa/lambda) <0.26, then Lambda light chain is defined as involved FLC, and Kappa light chain is defined as non-involved FLC
 - Difference between involved and unininvolved = Lambda LC-Kappa LC
- If the baseline ratio of (Kappa LC/Lambda LC) ≤ 1.65 and ≥ 0.26 , then “involved” and “non-involved” FLC can not be determined (ratio is normal), and maximum percent reduction from baseline for difference between two types of Serum FLC won’t be available.

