16.6. Appendix 6: Derived and Transformed Data

16.6.1. General

Multiple Measurements at One Analysis Time Point

 Mean of the measurements will be calculated and used in any derivation of summary statistics but if listed, all data will be presented. Participants having both High and Low values for Normal Ranges at any post-baseline visit for safety parameters will be counted in both the High and Low categories of “Any visit post-baseline” row of related summary Tables. This will also be applicable to relevant Potential Clinical Importance summary Tables.
Study Day

 Calculated as the number of days from First Dose Date: 
 Ref Date = Missing → Study Day = Missing Ref Date < First Dose Date → Study Day = Ref Date - First Dose Date Ref Date ≥ First Dose Date → Study Day = Ref Date - (First Dose Date) + 1
Change from Baseline

 Change from Baseline = Post-Baseline Visit Value - Baseline % Change from Baseline = $100 \times (\text{Post-Baseline Visit Value} - \text{Baseline}) / \text{Baseline}$ Maximum Increase/Decrease from Baseline = maximum (Increase/Decrease from Baseline) If either the Baseline or Post-Baseline Visit Value is missing, Change from Baseline and % Change from Baseline is set to missing
Date of Response

 For post-baseline disease assessments, the date of response (PR or better) is assigned to the latest date of disease assessments; for other response categories (MR, SD, NE, PD), the date of response is assigned to the earliest date of disease assessments.
Date of New Anti-Cancer Therapy

 Derived as the earliest date of new anti-cancer therapy, radiotherapy (where applicable) or cancer-related surgical procedure (where applicable) after date of study treatment discontinuation (date of last dose of study treatment). Missing or partial dates will be imputed for derivation of new anti-cancer therapy following rules specified in Section 16.7.2.1.

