16.6.3. Efficacy

Laboratory Parameters: Serum M-protein, Urine M-protein, Serum FLC

 If a laboratory value which is expected to have a numeric value for summary purposes, has a non-detectable level reported in the database, where the numeric value is missing, but typically a character value starting with '<x' or '>x' (or indicated as less than x or greater than x in the comment field) is present, the number of significant digits in the observed values will be used to determine how much to add or subtract in order to impute the corresponding numeric value. 
 Example 1: 2 Significant Digits = '< x ' becomes x – 0.01 Example 2: 1 Significant Digit = '> x' becomes x + 0.1 Example 3: 0 Significant Digits = '< x' becomes x – 1

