16.11.6. Efficacy Figures

Efficacy: Figures					
No.	Population	IDSL / Example Shell	Title	Programming Notes	Deliverable [Priority]
Response					
2.001	All Treated	Programming Note	Forest Plot – Overall Response Rate (ORR) Based on Investigator-Assessed Response	Report for Part 1 and Part 2, and combined Part 1 and Part 2: Similar to Figure 12.012 in BMA117159 (primary_02).	P-SAC [3], F-SAC [4]
2.002	All Treated	RE8b	Investigator Assessed Maximum Percent Reduction from Baseline in M-Protein (or FLC) Measurement	Report for: Part 1, Part 2, and combined Part 1 and Part 2; Summarize by: dose level (Refer to Section 5.1 for ordering of dose level and omit 1.92 mg/kg if data is not available) Total. Refer to mid205678 (primary_01) Figure 2.0030 for guidance	P-SAC [3], F-SAC [4]
Time-to-Event Endpoints					
2.003	All Treated	TTE10	Graph of Kaplan Meier Survival Curves for Duration of Response (GSK2857916 2.5 mg/kg)	Report for: 2.5 mg/kg doses only; Refer to Section 5.1 and use only code A, code D, and code H for dose level;	P-SAC [3], F-SAC [4]
2.004	All Treated	TTE10	Graph of Kaplan Meier Survival Curves for Time to Response (GSK2857916 2.5 mg/kg)	Report for: 2.5 mg/kg doses only; Refer to Section 5.1 and use only code A, code D, and code H for dose level;	P-SAC [3], F-SAC [4]
2.005	All Treated	TTE10	Graph of Kaplan Meier Survival Curves for Time to Best Response (GSK2857916 2.5 mg/kg)	Report for: 2.5 mg/kg doses only; Refer to Section 5.1 and use only	P-SAC [3], F-SAC [4]

Efficacy: Figures					
No.	Population	IDSL / Example Shell	Title	Programming Notes	Deliverable [Priority]
				code A, code D, and code H for dose level;	
2.006	All Treated	TTE10	Graph of Kaplan Meier Survival Curves for Progression Free Survival (GSK2857916 2.5 mg/kg)	Report for: 2.5 mg/kg doses only; Refer to Section 5.1 and use only code A, code D, and code H for dose level;	P-SAC [3], F-SAC [4]
2.007	All Treated	TTE10	Graph of Kaplan Meier Survival Curves for Time to Progression (GSK2857916 2.5 mg/kg)	Report for: 2.5 mg/kg doses only; Refer to Section 5.1 and use only code A, code D, and code H for dose level;	P-SAC [3], F-SAC [4]
2.008	All Treated	TTE10	Graph of Kaplan Meier Survival Curves for Overall Survival (GSK2857916 2.5 mg/kg)	Report for: 2.5 mg/kg doses only; Refer to Section 5.1 and use only code A, code D, and code H for dose level;	P-SAC [3], F-SAC [4]

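### The waterfall plot picks its marker by data availability, not measurability, so some patients with measurable disease only in urine or light chains can be drawn on a trace serum M-protein

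*SAP*

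**What the plan says.** Section 7.1.1.2 specifies a waterfall plot of each subject's maximum percent reduction, with BOR shown below the bars and colours marking the type of marker. The marker is chosen in three steps:

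- Step 1: "Plot Serum M-protein maximum percent reduction from baseline if data is available".
- Step 2: "If [1] is not feasible, plot Urine M-protein maximum percent reduction from baseline if data is available".
- Step 3: "If both [1] and [2] are not feasible, plot maximum percent reduction from baseline for difference between two types of Serum FLC", again subject to availability.

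The FLC step has a quality condition: with a normal kappa/lambda ratio at baseline, no FLC change is derived. The serum and urine steps have no such condition.

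Two other parts of the SAP bear on this:

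- Section 7.2.2.1, Table 5 footnote 4 (repeated under Table 6), sets baseline adequacy for progression-free survival and time to progression: "Adequate baseline assessment is defined as at baseline, a patient has at least one of the following measurements". The list is "Serum M-protein ≥ 0.5 g/dL (≥ 5 g/L) or b. Urine M-protein ≥ 200 mg/24h", or involved FLC of at least 10 mg/dL with an abnormal ratio.
- Section 16.6.3 covers serum M-protein, urine M-protein and serum FLC results reported only as below or above a limit. There, "the number of significant digits in the observed values will be used to determine how much to add or subtract in order to impute" a numeric value.

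The display is listed in Section 16.11.6 as Figure 2.002, "Investigator Assessed Maximum Percent Reduction from Baseline in M-Protein (or FLC) Measurement". It is planned for Part 1, Part 2 and both combined, at the primary and the final analysis. Section 7.2.1.2 refers Part 2 back to Section 7.1.1.2.

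**The concern.** Footnote 4 needs only one of three markers to be at a measurable level, so the SAP itself expects some patients to qualify on urine or FLC alone. The waterfall rule does not use that information. Any non-missing serum series with a non-zero baseline takes precedence, however small the values. The imputation rule can add to this by turning a non-detectable serum result into a small positive baseline.

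Percent change on a trace value says little about tumour burden. What is at stake is the subject-level picture of depth of response that accompanies ORR, the Part 2 primary endpoint. A responder's BOR could sit under a bar showing no reduction, or a bar could suggest a reduction that the measurable marker does not show.

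**Working it through.** The SAP states no figure here, so there is nothing to reproduce. The check applies its own rules to assumed patients. None of the values below are trial data.

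**Inputs from the SAP**
- Percent change (Section 16.6.1): 100 × (post-baseline − baseline) / baseline.
- Marker order (Section 7.1.1.2): serum, then urine, then FLC difference.
- Measurable levels (Table 5 footnote 4): serum ≥ 0.5 g/dL; urine ≥ 200 mg/24h; involved FLC ≥ 10 mg/dL (100 mg/L) with ratio < 0.26 or > 1.65.
- Below-limit values (Section 16.6.3): subtract 0.01, 0.1 or 1 for two, one or no digits.

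**Assumption:** each post-baseline value is the patient's lowest on treatment, because the figure plots the maximum reduction.

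**Marker order as written, against first measurable marker in the same order**

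| Assumed patient | SAP rule plots | First measurable marker |
|---|---|---|
| A. Serum 0.2 to 0.2 g/dL; urine 1000 to 100 mg/24h | Serum: (0.2 − 0.2)/0.2 = 0% | Urine: (100 − 1000)/1000 = −90% |
| B. Serum 0.2 to 0.1; urine 1000 to 1000 | Serum: (0.1 − 0.2)/0.2 = −50% | Urine: 0% |
| C. Serum 0.3 to 0.3; kappa 500 to 50 mg/L, lambda 10 to 10 mg/L; urine not measurable | Serum: 0% | FLC difference 490 to 40: (40 − 490)/490 = −91.8% |
| D. Serum 2.0 to 0.5; measurable | Serum: (0.5 − 2.0)/2.0 = −75% | Serum: −75% |
| E. Serum baseline 0; urine 1000 to 100 | Serum change cannot be computed; read as not feasible, so urine: −90% | Urine: −90% |

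In C the baseline ratio is 500/10 = 50, so kappa is the involved chain and, at 500 mg/L, is above 100 mg/L.

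**Effect of the imputation rule on a non-detectable serum baseline**
- '<0.10' (two digits): 0.10 − 0.01 = 0.09. Non-zero, so serum is plotted, at 0% if it stays non-detectable.
- '<0.5' (one digit): 0.5 − 0.1 = 0.4. Non-zero, so serum is plotted.
- '<0.1' (one digit): 0.1 − 0.1 = 0.0. Percent change is undefined, as in E.
- '<1' (no digits): 1 − 1 = 0. As in E.

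Whether a non-detectable serum result displaces a measurable marker therefore depends on the reporting precision of the laboratory. The two rules disagree in A, B and C, where the serum baseline is above zero but below 0.5 g/dL and the measurable disease is elsewhere. They agree in D and E.

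**The case against.** The strongest reply is that steps 2 and 3 turn on feasibility, which is wider than availability. A study team could treat a trace serum M-protein as not feasible and move on. That reading does rescue a zero or missing serum baseline. It does not clearly rescue a small positive one: step 1 tests only whether data are available, and the SAP never says what makes a step infeasible.

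Several stronger readings are tempting but not supported:

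- **That all urine-only and light-chain patients are misplotted.** Only those with a non-zero, or imputed non-zero, serum baseline below 0.5 g/dL are. The SAP does not show that every such patient has serum results, or in what form non-detectable results are recorded, so it cannot be said that steps 2 and 3 would rarely be reached.
- **That a baseline imputed to zero breaks the plot.** The serum change is then undefined, step 1 is plausibly not feasible, and the order moves on. The SAP does not spell this out.
- **That assay noise would give a +100% bar.** The figure takes the maximum reduction, so every on-treatment serum value would have to be at least double the baseline.
- **That the response results are affected.** BOR and ORR come from investigator assessment under the IMWG criteria (Section 7.1.1.1), and no test, interval or stopping rule uses the plot.

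It is also fair to say that footnote 4 was written for progression censoring, and that the colour coding and the printed BOR would help a reader notice an odd bar. But colour shows which marker was used, not whether it was measurable. Section 16.11.6 cites another study's figure for guidance. That figure is not available here and cannot stand in for a stated rule.

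**Conclusion.** The point holds in a limited form. As written, the rule can plot a patient on a serum M-protein that the SAP's own thresholds would not count as measurable, and the resulting bar can understate or overstate the change. In the assumed examples the gap is 90 percentage points (A), 50 in the opposite direction (B) and about 92 (C).

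The SAP does not give the number of affected patients. Purely as an assumption, if 10% to 25% of the roughly 40 planned subjects (about 12 in Part 1 and 28 in Part 2) were measurable only by urine or FLC, that would be 0.10 × 40 = 4 to 0.25 × 40 = 10 patients. This is a ceiling, because only those with a small non-zero serum baseline are affected.

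The consequence is confined to Figure 2.002, a descriptive display whose bars may disagree with the BOR below them. It is worth correcting because the correction is cheap and uses thresholds that the SAP already contains. It is not a threat to the trial's conclusions.

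**What to change.** In Section 7.1.1.2, keep the order and replace availability with measurability at baseline, by reference to Table 5 footnote 4:

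1. Serum M-protein, if baseline is ≥ 0.5 g/dL.
2. Otherwise urine M-protein, if baseline is ≥ 200 mg/24h.
3. Otherwise the FLC difference, if involved FLC is ≥ 10 mg/dL with ratio < 0.26 or > 1.65.
4. Otherwise no bar, with a footnote to Figure 2.002 identifying subjects not plotted because no marker was measurable.

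Add that a baseline imputed from a below-limit result under Section 16.6.3 does not count as measurable. The feasibility wording then becomes unnecessary.

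The cost is a short edit to the text and one condition in the figure program. No endpoint or other analysis changes. The downside is that a few subjects without any measurable marker lose their bar in a plot described as showing each subject, which is why the footnote is needed.
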